## DATA ANALYSIS AND STATISTICAL METHODS

### I. Statistical Analysis

Specific Aim 1 is to determine if combined pharmacotherapy of escitalopram + celecoxib will result in earlier and/or improved affective responses compared to escitalopram + PBO. Additionally, Specific Aim 1 seeks to control for pain perception in this analysis. For this aim, the patients in the two treatment arms will be compared on HAM-D, HAM-A, MADRS, BDI, and BAI scores. This will be accomplished with an analysis of covariance conducted at weeks 1, 2, 4 and 8. Baseline mood scores and McGill Pain Inventory scores will be used as covariates. In addition, the number of patients who are and are not classified as remitters at week 8 (those having a HAM-D score of 7 or less) will be tallied and cross-referenced with treatment group (escitalopram + celecoxib or escitalopram + PBO). The frequencies in the resulting 2-by-2 contingency table will be analyzed with the Pearson Chi-Square Test for Association.

For Specific Aim 2, dealing with treatment safety and tolerability, the numbers of patients who do and do not experience adverse events at weeks 1, 2, 4, and 8 will be tallied and cross-referenced with treatment group. The frequencies in the resulting 2-by-2 contingency table will be analyzed with the Pearson Chi-Square Test for Association. Additionally, to understand whether any pharmacodynamic interaction exists between escitalopram and celecoxib, blood levels of escitalopram and celecoxib drawn at weeks 4 and 8 will be compared for patients in the two treatment groups with an analysis of covariance using baseline levels as a covariate. If there is no pharmacokinetic interaction then we expect that there will be no statistically significant results for these analyses.

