All statistical analyses will be conducted using the latest version of SPSS software for Windows. If a subject drops out after completing 6 weeks on active medication (after randomization), we will use the last observation carried forward (LOCF method) to analyze the data. If a subject has completed at least one week on active medication after randomization, but drops out of the study at any time between week-1 and week-8, s/he will be included in the intent-to-treat analysis. Since this project seeks to provide proof-of-concept in bipolar depression, and is therefore exploratory in nature, we propose the tests of significance use a 0.05 alpha level. However, if this proposal develops further we may adjust our desired level of statistical significance to be in line with the number of tests so that the family wise Type I error rate could be held at 5%. This issue will be considered in the future.

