## II. Determination of Sample Size

Although a number of tests of statistical significance are planned for the proposed study, our required sample size is being based upon the primary outcome of treatment effect (Specific Aims 1). In looking at differences in mean HAM-D scores from the studies by Akhondzadeh et al. 5 and Mueller et al. 6 we found that the effect sizes of an antidepressant + anti-inflammatory agent over an antidepressant + placebo at week 3 of treatment were 0.53 and 0.52, respectively. In the proposed research we anticipate that the effect size will be slightly higher due to the fact that variation in depression scores attributable to baseline levels and pain perception will be eliminated in an analysis of covariance. Hence, we anticipate that the effect size will be about 0.60 for escitalopram + celecoxib over escitalopram + PBO. As noted earlier, we anticipate that the drug combination will lead to a therapeutic response that is earlier than what is normally seen at week-3 of treatment. We thus expect to see a treatment effect at week-2 of therapy, and expect that the magnitude of the effect will increase over the course of the study. The increasing separation between the different treatment groups is similar to what was found in the studies mentioned above which observed rising treatment effects during the course of therapy. From this, our computations indicate that a sample size of 45 patients per group will provide 80% power for an analysis of covariance to detect an effect size of 0.60 at week-2 of therapy using a 0.05 level of significance. Thus, a total of 90 patients completing treatment will be acquired for the proposed work. 30 of the total patients will be enrolled and randomized at our sister site in Munich, Germany. Given that the therapeutic effect size is expected to increase over time, the proposed sample size will be adequate throughout the course of the study. Subjects lost to attrition will be replaced.

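### The set called intent-to-treat admits drop-outs only after a week on medication, so first-week leavers have no stated place in the efficacy and remission analyses

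*Combined protocol and SAP*

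**What the plan says.** All references are to the combined protocol and SAP.

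- **Analysis set (I. Statistical Analysis).** The condition is "If a subject has completed at least one week on active medication after randomization". A patient who meets it and leaves between week 1 and week 8 is covered by "s/he will be included in the intent-to-treat analysis". This is the only definition of the set. Nothing is said about a patient who leaves before completing a week.
- **Missing data (same section).** "If a subject drops out after completing 6 weeks on active medication (after randomization), we will use the last observation carried forward". The rule stops there, and no method is given for earlier drop-outs.
- **Remission (same section, Aim 1).** The 2-by-2 table tallies "the number of patients who are and are not classified as remitters at week 8" by arm, for a Pearson chi-square test. It names no analysis set and does not classify patients without a week-8 score. Remission at 8 weeks is one of the three components listed under Primary Endpoint.
- **Replacement and target (II. Determination of Sample Size).** "Subjects lost to attrition will be replaced", and "Thus, a total of 90 patients completing treatment will be acquired for the proposed work".
- **Drop-out (Study Design).** The plan expects 10%, with no split by arm or by time.

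No analysis of all randomised patients and no sensitivity analysis for missing data is planned.

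**The concern.** Randomisation makes the arms comparable at the moment of assignment. A condition met afterwards, such as a week on medication, can break that comparability, because the chance of meeting it may depend on the assigned treatment. The label intent-to-treat tells readers that this has been avoided, and under this definition it has not.

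First-week exits need not be random. The Criteria for Subject Termination include a suicide attempt or serious deterioration, so an early exit can itself be a failure of efficacy. The section on bleeding diathesis monitoring recognises a possible risk from combining an SSRI with a COX-2 inhibitor, so early tolerability could differ between arms. A patient who left in the first week for either reason would ordinarily count as not in remission at week 8. Followed as written, the plan gives that patient no place in the comparison, while recruitment continues until 90 patients have completed. What is at stake is the denominator of the remission rates and the claim that the arms are compared as randomised.

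**Working it through.** **1. The plan's own figure.** Inputs from II. Determination of Sample Size: "80% power for an analysis of covariance to detect an effect size of 0.60 at week-2 of therapy using a 0.05 level of significance", with 45 per group. I. Statistical Analysis adds "we propose the tests of significance use a 0.05 alpha level", without stating sidedness. Normal approximation, two-sided: n = 2 × (1.960 + 0.842)² / 0.60² = 43.6, so 44 per group. The two-sample t-test gives 44.6, so 45, with 80.4% power at 45. An ANCOVA F-test with two covariates gives 80.3%. A one-sided test would need only 35, so the plan is evidently two-sided. The stated 45 per group reproduces; the problem is who is analysed, not the count.

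**2. Effect of leaving early leavers out of the remission table.** The documents give no remission rate and no early loss by arm, so everything in this step is assumed. Let r be the proportion in remission among all randomised patients, with early leavers counted as non-remitters and r equal in both arms. Let d be the proportion of an arm lost in the first week and left out. The analysed rate in that arm is r / (1 − d).

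With d = 10% in one arm and 0% in the other:

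| r (both arms) | Analysed, arm with 10% loss (r / 0.9) | Analysed, arm with no loss | False difference | Chance of a significant result favouring the arm with more loss |
|---|---|---|---|---|
| 30% | 33.3% | 30.0% | 3.3 points | 5.2% |
| 40% | 44.4% | 40.0% | 4.4 points | 6.2% |
| 50% | 55.6% | 50.0% | 5.6 points | 7.6% |

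The last column should be 2.5% when there is no true difference. It assumes 45 analysed per arm and uses Φ{[Δ − 1.96 √(2p̄(1 − p̄)/45)] / √([p₁(1 − p₁) + p₂(1 − p₂)]/45)}. For r = 40%: (0.0444 − 1.96 × 0.1041) / 0.1040 = −1.53, and Φ(−1.53) is about 0.06. On 45 patients the false difference amounts to 0.033 × 45 = 1.5 up to 0.056 × 45 = 2.5 remitters.

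**3. Equal loss.** With d = 5% in both arms, rates of 30%, 40% and 50% are reported as 31.6%, 42.1% and 52.6% (r / 0.95). There is no false difference when true remission is equal, but both rates are too high.

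**4. How large d could be.** The 10% in Study Design covers the whole study, so it is a ceiling for first-week loss. A split of 10% versus 0% averages 5%, that is, half of the expected total falling in the first week and all of it in one arm. A split of 20% versus 5% would give 7.9 points at r = 40% (50.0% against 42.1%), but it averages 12.5%, above the plan's total.

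**5. Numbers and power if everyone is kept.** For 90 completers at 10% drop-out: 90 / 0.9 = 100 randomised. Study Design already foresees 70 at the main site and about 30 at the sister site, which is 100. If leavers gain no benefit and the SD is unchanged, the effect becomes 0.60 × (1 − q), where q is the proportion leaving:

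- q = 5%: effect 0.57; 50 per arm needed for 80% power; power at 50 per arm 80.6%.
- q = 10%: effect 0.54; 55 per arm needed; power at 50 per arm 76.2%.

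**The case against.** The best reply is that the sentence is one of inclusion. It says who is in, and no sentence says that first-week leavers are out. The remission tally names no set and could be read as counting anyone without a week-8 score as a non-remitter. Both arms start escitalopram at randomisation, so much early intolerance may be common to both, and the Background describes celecoxib add-on as safe and well tolerated in earlier studies. Adverse events are compared by arm under Aim 2, so early intolerance is not lost from the safety tables. The plan also calls itself exploratory proof of concept.

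Much of this stands, and it rules out several stronger readings that a reader might infer:

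- *A patient who stops the blinded capsule on day 4 but attends week 1 is excluded.* Not established. Escitalopram is also active medication, and the sentence concerns patients who drop out of the study.
- *Leavers are expressly removed from the remission table.* The text does not say so. Their place there is undefined.
- *Replacement discards the leaver's data or substitutes a patient who tolerates treatment.* The replacement sentence says neither. Drop-outs after week 1 are expressly kept, and a replacement may also leave early.
- *The bias favours celecoxib.* That needs more first-week loss on celecoxib, and the documents give no loss by arm.
- *Ten per cent of 45, or 4 to 5 per arm, are first-week exits.* That figure is drop-out over the whole study. It accompanies a plan to enrol about 80 for 70 randomised, so it may even include losses before randomisation.

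What the reply does not remove is the condition itself. It is the only definition of the set, it turns on exposure after randomisation, and nothing elsewhere brings the first-week leaver back in. Exploratory status bears on how strongly the tests are read, not on who is analysed.

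**Conclusion.** The point holds. The set labelled intent-to-treat depends on completing a week on active medication, so it is not intent-to-treat, and first-week leavers have no stated place in the efficacy or remission analyses. The direction and size of any bias cannot be read from the documents. It runs toward whichever arm loses more patients early, provided those patients would not have remitted. On the assumptions shown, 10% versus 0% early loss gives a false difference of 3.3 to 5.6 points, or roughly two remitters in 45. With equal loss the harm is overstated remission rates in both arms. This is a modest but avoidable weakness in a primary-endpoint component, and the change should be made.

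Two neighbouring gaps bear on the same wording. Drop-outs between weeks 1 and 6 are in the set, but LOCF does not reach them, so their week-8 value is undefined. Study Design requires 8 weeks for a completer and Study Procedures at least six; the two must be reconciled, because they decide who counts toward the 90.

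**What to change.** In I. Statistical Analysis:

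- Define the intent-to-treat set as all randomised patients, by assigned arm, and name it as the set for the Aim 1 tests.
- Count every randomised patient with no week-8 HAM-D as a non-remitter in the 2-by-2 table.
- Analyse HAM-D with all available post-baseline ratings, whatever the time on drug. A repeated-measures mixed model is one suitable way. It cannot help a patient with no post-baseline rating, so report the number of such patients by arm.

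In II. Determination of Sample Size, state that patients enrolled to replace leavers are added to the analysis while the leavers stay in it.

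**Cost.** Mainly SAP wording. Remission rates may look slightly lower. The 100 patients already foreseen would cover 90 completers at 10% drop-out. If leavers gain no benefit, power at 50 per arm would be about 81% with 5% leaving and 76% with 10% leaving; restoring 80% in the latter case would take 55 per arm.

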## II. Determination of Sample Size

Although a number of tests of statistical significance are planned for the proposed study, our required sample size is being based upon the primary outcome of treatment effect (Specific Aims 1). In looking at differences in mean HAM-D scores from the studies by Akhondzadeh et al. 5 and Mueller et al. 6 we found that the effect sizes of an antidepressant + anti-inflammatory agent over an antidepressant + placebo at week 3 of treatment were 0.53 and 0.52, respectively. In the proposed research we anticipate that the effect size will be slightly higher due to the fact that variation in depression scores attributable to baseline levels and pain perception will be eliminated in an analysis of covariance. Hence, we anticipate that the effect size will be about 0.60 for escitalopram + celecoxib over escitalopram + PBO. As noted earlier, we anticipate that the drug combination will lead to a therapeutic response that is earlier than what is normally seen at week-3 of treatment. We thus expect to see a treatment effect at week-2 of therapy, and expect that the magnitude of the effect will increase over the course of the study. The increasing separation between the different treatment groups is similar to what was found in the studies mentioned above which observed rising treatment effects during the course of therapy. From this, our computations indicate that a sample size of 45 patients per group will provide 80% power for an analysis of covariance to detect an effect size of 0.60 at week-2 of therapy using a 0.05 level of significance. Thus, a total of 90 patients completing treatment will be acquired for the proposed work. 30 of the total patients will be enrolled and randomized at our sister site in Munich, Germany. Given that the therapeutic effect size is expected to increase over time, the proposed sample size will be adequate throughout the course of the study. Subjects lost to attrition will be replaced.

